### **3.7. Procedure for study drug accountability**

The investigator is responsible for drug accountability. The pharmacist or another authorized employee of the trial site must receive the study drugs, check the inventory, and fill out the drug receipt confirmation form. A copy of this form remains at the trial site, and the original must be sent to the sponsoring company or an organization authorized by it. In the course of the study, the pharmacist or another authorized employee of the trial site keeps records of the release of study drugs in a special log on drug release. The following information is recorded in this log for each volunteer:

- Volunteer's initials.
- Volunteer No.
- Study drug code (assigned to a volunteer during randomization).
- Time and date when the study drug was dispensed.
- Batch numbers of dispensed drugs.
- Expiry date of the dispensed drugs.
- Time and date when the study drug packages were returned.

The drug release log is maintained and stored in such a manner that none of unauthorized persons have access to the information contained in this log.

All primary and secondary packaging of study drugs, both used and unused, should be stored at the trial site for accounting. After the end of the study, the investigator must return all used or unused packages to the study Sponsor or its authorized organization.

### **3.8. Storage of randomization codes and unblinding procedures**

The randomization scheme (randomization list in the IWRS system) will only be known to the Sponsor, the investigators will not be able to influence the group selection, to which a specific volunteer is assigned during randomization.

---

Strictly confidential. Proprietary Information.  
[name]

If any of the members of the research team learn about accidental / intentional disclosure of the information as to which group a volunteer was randomized into, he/she should immediately notify the sponsor company.

### **Procedure for unblinding of randomization codes**

In a case of a medical emergency (including pregnancy of a female volunteer), for which knowledge of the nature of study investigational drug is critical to further treatment, the investigating physician may send a request to the sponsor for disclosure of the code for this volunteer. Unblinding can be performed only if it is fully justified. In other cases, especially when an emergency situation is not clearly associated with the study drug, the problem should be solved based on the assumption that a volunteer is receiving an unauthorized study drug.

At the request of the Principal Investigator, the sponsor company will inform the investigating physician on which vaccine a volunteer is receiving — the emergency unblinding procedure for the assigned vaccine through electronic randomization system (IWRS). Instructions for emergency unblinding procedure will be provided to the trial site along with guidance for use of IWRS.

If it is not possible to contact IWRS for emergency unblinding, the Principal Investigator shall contact the Sponsor's representative.

Emergency unblinding of the study therapy should be described and justified in volunteer's primary documentation and recorded in the appropriate section of the CRF.

### **3.9. The list of all data recorded directly in the CRF and considered as source data**

All medical data about volunteers must first be recorded in the source documents on a paper or electronic medium and only then entered into the CRF.

Baseline data is described in detail in Section 12.1.

## **4. SELECTION AND EXCLUSION OF STUDY SUBJECTS**

### **4.1. Subject inclusion criteria**

1. Signed and dated volunteer's informed consent for participation in the study.
2. Men and women from 18 to 60 years old.
3. Healthy volunteers without signs of acute or chronic disorders, without history of chronic respiratory, cardiovascular, nervous system disorders, hepatic or renal disorders.
4. Previously not immunized, or previous influenza immunization occurring  $\geq$  12 months before this study.
5. Subjects without history of influenza within  $\geq$  12 months before this study.

Strictly confidential. Proprietary Information.  
[name]

6. Consent of volunteers (men and women) to use adequate methods of contraception (cervical caps with spermicide, diaphragms with spermicide, condoms with spermicide, intrauterine devices, oral contraceptives) or full abstinence for the whole period of the study.

#### **4.2. Subject non-inclusion criteria**

*Specific:*

1. Contraindications listed in the protocol and prescribing information for inactivated influenza vaccines:
  - acute infections and non-communicable disorders, including the period of convalescence of at least one month from the time of clinical and laboratory evidence of recovery;
  - hepatitis or meningococcal infection occurred less than 6 months after recovery;
  - exacerbations of chronic disorder or decompensated disorders that may impact the study (organic central nervous system disorders, decompensated cardiovascular disorder, acute renal or hepatic failure);
  - malignant neoplasms (including hematological disorders);
  - primary immunodeficiency (laboratory-confirmed);
  - HIV infection or HIV-associated disorders;
  - systemic disorders of connective tissue;
  - haemophilia (and other blood coagulation disorders);
  - severe neurological disorders;
  - Guillain–Barré syndrome (post infection demyelinating polyradiculoneuropathy of autoimmune nature with peripheral limb muscle palsy related to inflammation and destruction of myelin sheath of peripheral nerves; may acquire an ascending nature, involving muscles of face, pharynx, larynx);
  - history of severe vaccine-associated reactions (body temperature exceeding 38.5 °C) or local reactions (hyperemia and/or oedema at the site of injection of over 5 cm in diameter);
  - history of severe allergic disorders (angioedema, polymorphic exudative erythema, serum disease, etc.);
  - hypersensitivity to chicken protein or vaccine components;
  - blood and components transfusion within the last 6 months.
2. Indications for immunomodulating therapy.
3. Body temperature over 37.0 °C at screening or before injection.
4. Potential evidence of a chronic infection (periodic episodes of fever within the last 6 months), or antiviral (and/or antibacterial) treatment indicated.
5. History of disorders or conditions, which, according to investigator's judgment may impact the thermal regulation (chronic infections, neuroendocrine disorders [thyrotoxicosis, pheochromocytoma, etc.], climacteric syndrome, malignant hyperthermia, CNS disorders,

---

Strictly confidential. Proprietary Information.  
[name]

malignant neoplasm, connective tissue disorders, systemic vasculitis, and information on excessive physical stress or work-rest regimen deviations [within the last 2 months: night shifts, significant change of time zones, overheating]).

6. Use of antipyretics (including non-steroidal anti-inflammatory drugs and anilides) within 24 hours before randomization.
7. Surgical interventions within less than 90 days before the screening visit.
8. Systolic blood pressure of over 130 mm Hg or less than 100 mm Hg and/or diastolic blood pressure of over 90 mm Hg or less than 60 mm Hg.
9. Any other disorder, which, in the opinion of the investigator, may prevent inclusion of the volunteer due to safety reasons or may impact the study results.

General:

10. Pregnant and nursing women.
11. Lack of ability to visit daytime inpatient facility according to the study schedule, unavailability for adequate follow-up of the volunteer.
12. Body mass index of less than 18.5 or over 30.0 kg/m^2 based on the weight-height Quetelet's index.
13. Participation in another clinical study of medicinal drugs within 3 months before the start of this study.
14. Mental, physical, or other reasons which prevent adequate assessment of own behavior and prevent from meeting the study protocol conditions.
15. History of narcotic and/or drug abuse, and/or inhalant addiction, current signs of alcoholic intoxication.
16. Intake of at least 5 alcohol units per week or history of alcohol, drug, or medicinal product abuse. One alcohol unit corresponds to 360 ml of beer, 120 ml of wine, or 30 ml of a strong alcoholic beverage.
17. Suspected lack of compliance with treatment or inability to undergo treatment and observe the limitations according to the study protocol.
18. Volunteers acknowledged by the court to be disabled or under guardianship.
19. Any other conditions that make the volunteer ineligible for the study according to a justified opinion of the study doctor or Sponsor.

#### **4.3. Subject exclusion criteria**

Volunteer exclusion criteria are provided in Section 3.6.

---

Strictly confidential. Proprietary Information.  
[name]

## 5. TREATMENT (VACCINATION) OF SUBJECTS

### 5.1. Treatment (vaccination) with study drugs

Name, description, and dosages of vaccines are provided in Section 3.4.

The investigator or an authorized person will be responsible for controlling the administration of the vaccine to enrolled study participants in accordance with the procedures defined in this study protocol. All vaccines will be administered only by staff members that have the right to perform this function in accordance with applicable local laws and trial site rules.

Detailed instructions for preparing and administering the vaccine will be provided to investigators in additional documentation prior to study initiation.

The vaccine cannot be used in the following cases:

- when the ampoule is damaged;
- when foreign matter is present;
- in case of a missing label or missing information from it;
- in case of violation of storage conditions.

**Dosing:** All the vaccines used in the study are administered as a single intramuscular injection of 0.5 ml (1 dose) into the upper third of the outer surface of the shoulder (the deltoid muscle). The exact anatomical site of each injection must be carefully recorded in the medical record and transferred to the CRF.

Standardized immunization practices should be strictly followed, and the vaccine should be administered intramuscularly. **DO NOT INJECT intravenously.** Before vaccine administration, the vaccination site should be disinfected with an appropriate skin disinfectant (70 % ethyl alcohol). Wait until the skin is dry. After vaccine injection, the vaccination site shall be wiped again with 70 % ethyl alcohol.

As with all injectable vaccines, trained medical personnel with proper medical treatment should be available if anaphylactic reactions should occur after vaccine administration. For example, a 1:1,000 solution of epinephrine, diphenhydramine, and/or other drugs for the treatment of anaphylaxis should be available.

In case any foreign particles are detected, and/or any changes in the appearance of the vaccine are observed, the vaccine should not be administered to the participant, and the issue should be reported to the manufacturer. The vaccine should not be discarded without sponsor's permission. Any unused medication or waste must be disposed of in accordance with the local regulations.

#### **Administration error and overdose:**

This study is designed for a one-time intramuscular injection of vaccine. The erroneous administration of vaccine is defined as the administration of the vaccine under study in a dosage that does not comply with the instructions or inappropriate mode of administration. An overdose of study vaccine (accidental or deliberate) is defined as the administration of a dosage exceeding a

---

Strictly confidential. Proprietary Information.  
[name]

single recommended dose of study vaccines.

Any erroneous administration or an overdose of study vaccine must be registered as an adverse event, and if the erroneous administration of the vaccine or an overdose cause a severe response, the Sponsor should be informed within 24 hours.

## **5.2. Drugs / treatments that are permitted or not permitted before and / or during the study**

### **5.2.1. Contraindicated drugs and treatments**

The use of the following drugs (regardless of the mode of administration) and treatment methods is prohibited during the study:

- only at screening and on the day of immunization:
  - antipyretics (including non-steroidal antiinflammatory drugs and anilides);
  - any drugs or food supplements which, according to the investigator's judgment, may affect the body temperature of the volunteer (including caffeine);
  - physiotherapeutic procedures.
- For the whole period of the study:
  - medicinal products suppressing central nervous system functions (barbiturates, opiates, sedative drugs), tranquilizers, neuroleptics, tricyclic antidepressants etc.;
  - cytotoxic drugs;
  - anticoagulants (including warfarin), antiaggregants (including clopidogrel, acetylsalicylic acid).

Hormonal contraceptives or hormone replacement therapy is only allowed if the female volunteer has been on a stable dosing regimen maintained for at least 6 months before the screening visit and remains on a stable dosing regimen for the whole study period.

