Only the subjects without any intercurrent conditions within the first five days after immunization were included in the system reactions analysis: in total 29 of the 30 subjects from the group Grippol® Quadri, 28 of 30 subjects from the group Grippol® Plus, and 29 subjects from the Placebo group. During the evaluation of the reactogenicity, the general reactions were detected in the group Grippol® Quadri in 20.7 % of the subjects, in the group Grippol® Plus in 3.6 % of the subjects, and in the Placebo group in 10.3 % of the subjects. Among the general reactions recorded during the study, there were the following: rise in body temperature above 37 °C, malaise, headache, nausea, myalgia / arthralgia. The most common general reaction in the group Grippol® Quadri was the development of headache — in 13.8 % of the subjects, whereas in the group of Grippol® Plus and in the Placebo group headache was observed only in 3.6 % and 3.4 % of the subjects respectively. The rise in body temperature above 37 °C was recorded in 6.9 % of subjects in the group Grippol® Quadri (within subfebrile with a maximum registered value of 37.2 °C), and also in 6.9 % of subjects in the Placebo group (within subfebrile with a maximum registered value of 37.5 °C). All the occurred systemic reactions were regarded as mild. During the comparative evaluation, there was no evidence of the statistically significant difference between the proportion of mild, moderate, and severe local reactions in the Grippol® Quadri group, Grippol® Plus group, and Placebo group ( $p = 0.102$  and  $p = 0.470$  respectively).

Strictly confidential. Proprietary Information.  
[name]

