### **5.2.2. Permitted drugs and treatments**

All unprohibited products and treatments are allowed.

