#### **Recording of thermometry results and complaints of a study subject in a volunteer's self-observation diary:**

A study subject will record axillary temperature in a self-observation diary every day, in the morning and in the evening, starting from Visit 1 after immunization and till Visit 7 (further measurements — depending on condition). He/she will also record concomitant therapy and complaints related to his/her medical condition during the day (if any); to do so, a subject will be offered to answer the

Strictly confidential. Proprietary Information.  
[name]

following question in the volunteer's diary in writing:

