**Assessment of local and systemic reactions to vaccine administration (reactogenicity)**

For assessment of local and systemic reactions to vaccine administration, the results of daily examinations are recorded in a Case Report Form and an Outpatient Medical Record for each subject. Particular attention is paid to symptoms corresponding to clinical manifestations of influenza, allergic and neurological reactions. A local reaction is evaluated by the diameter of a hyperaemic skin area at the injection site, skin tenderness and oedema, and enlargement of regional lymph nodes.

The assessment is performed before immunization, 2 hours after immunization, then once a day for 5 post-immunization days; thermometry is mandatory. Subjects who responded to the vaccination are monitored until these reactions pass off completely. In case of development of any unusual reactions the subject will be examined by an appropriate specialist. The following parameters are used for evaluation of tolerability of the study drugs.

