***Systemic reactions:***

1. Increase of body temperature over 37 °C
2. Malaise
3. Headache
4. Sleep disturbance
5. Appetite disturbance
6. Nausea
7. Vomiting
8. Abdominal pains
9. Stuffy nose

---

Strictly confidential. Proprietary Information.  
[name]

10. Cough
11. Pharynx hyperaemic
12. Increased sweating
13. Tremor
14. Myalgia, arthralgia.

The nature and duration of immunization reactions in vaccinated subjects is compared upon interpretation of all study materials. An analysis of this data will make it possible to formulate a conclusion and resolve the issue of tolerability of study vaccines.

The course of the post-immunization period is assessed as smooth or complicated. Complicated course of the post-immunization period is considered as integration of intercurrent diseases after immunization. The absence of intercurrent diseases is considered as smooth post-immunization period. Fever responses were classified by temperature increase as follows: mild (low-grade fever up to 37.5 °C), moderate (temperature rise from 37.6 °C to 38.5 °C), and severe (temperature rise above 38.6 °C).

Local immunization reactions are classified as mild, moderate, and severe. Erythema without infiltration up to 50.0 mm in diameter at the injection site or infiltration up to 25.0 mm in diameter is estimated as a mild local reaction; erythema with a diameter more than 50.0 mm or an infiltrate with a diameter 26.0 to 50.0 mm was estimated as a moderate local reaction; infiltration more than 50.0 mm in diameter was estimated as a severe local reaction (Methodological Guidelines MU 3.3.2.1758-03 "Methods for determination of quality indicators of immunobiological products for prevention and diagnostics of influenza"). When the reaction is free of redness and/or infiltration, the reaction severity is accepted as indeterminate.

Local reactions will be assessed in all subjects, since local reactions were directly related to the administration of the vaccine.

Occurrence of general symptoms on the first 3 days after (and even on the day of immunization) may be associated with immunization (systemic reactions). However, it does not rule out their causal relationship with diseases, accidentally occurring within the first days of post-immunization period.

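### Fever is graded on recorded temperature alone while most antipyretics are allowed from Day 1, and no planned table uses the recorded drug intake, so fever rates may be understated

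*Combined protocol and SAP*

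**What the plan says.** **Medication rule.** Section 5.2.1 bars antipyretics, with NSAIDs and anilides named, "only at screening and on the day of immunization". They share that list with other products that may alter body temperature. Section 4.2 (criterion 6) also excludes anyone who took them in the 24 hours before randomization. Acetylsalicylic acid is barred for the whole study, because it is listed as an antiaggregant. Section 5.2.2 then says: "All unprohibited products and treatments are allowed". So every other antipyretic is allowed from Day 1.

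**Fever assessment.** Under Section 7.2, reactions are assessed before vaccination, two hours after it, and "then once a day for 5 post-immunization days; thermometry is mandatory". A temperature above 37 °C is the first systemic reaction listed. The grading rule opens "Fever responses were classified by temperature increase as follows", and the three grades that follow are temperature bands and nothing else.

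**What is recorded.** Volunteers log axillary temperature morning and evening until Visit 7. On the same diary, "He/she will also record concomitant therapy". Table 2 also has concomitant therapy recorded at every visit.

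**What is analysed.** The safety analysis in Section 8.1 is descriptive. It tabulates volunteers with local and general reactions by severity and duration. It has no rule for a temperature taken after an antipyretic and no table of antipyretic use by group.

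**The concern.** The protocol treats these drugs as distorting temperature, since it keeps them away from the baseline and vaccination-day readings. From Day 1 they are allowed, yet the readings enter the tables at face value. Section 7.2 does deal with one confounder of systemic reactions: general symptoms are set aside when an intercurrent infection could explain them. It has no counterpart for antipyretics.

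Reactogenicity is in the study title and is a stated purpose, and fever is one of its few instrument-measured components. The highest Phase I temperature in the Quadri group was 37.2 °C (Section 1.2), only 0.2 °C above the cut-off, so a small drug effect could move a reading across it. If rates are understated, the tolerability profile looks better than it is. If the understatement differs by group, the comparison with the trivalent vaccine is affected too.

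**Working it through.** **1. The rules side by side**

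| | Day 0 | Days 1–5 |
|---|---|---|
| Antipyretics, NSAIDs, anilides | barred | allowed, except acetylsalicylic acid |
| Temperature assessed as a reaction | yes | yes, daily |
| Drug intake recorded | yes | yes |
| Intake used in a planned fever table | no | no |

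On five of the six days, a lowered reading is handled like any other. For a fever that is treated there are three outcomes:

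- It exceeds 37 °C at some reading, before treatment or between doses: it is counted.
- It is counted, but the peak is lower or it ends sooner: the grade or duration may be understated.
- It is suppressed at every reading: it is missing from the temperature line.

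**2. What Phase I shows (Section 1.2, smooth-course denominators 29 Quadri, 28 Plus, 29 placebo)**

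The plan's own figure first. Systemic reactions of 20.7 % and 3.6 % correspond to 6/29 and 1/28. Fisher's exact test gives p = 0.102, the stated value. (The sentence giving that p-value says local reactions, but it stands in the systemic paragraph and the systemic counts reproduce it.)

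The same test on the relevant symptoms:

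- Headache: "The most common general reaction in the group Grippol® Quadri was the development of headache — in 13.8 % of the subjects", that is 4/29, against 3.6 %, or 1/28, for Plus: p = 0.35. Using Table 1, and assuming that the likely and possible cases are different people, 5/30 against 1/30: p = 0.19.
- Temperature above 37 °C: 2/29 (6.9 %) for Quadri and 2/29 for placebo, p = 1.0. None is reported for Plus; taking 0/28, p = 0.49.

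The headache estimates lean towards Quadri, but on four cases against one.

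**3. Illustration of masking**

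The documents give no rate of antipyretic use, so the masked shares below are assumptions.

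Observed rate = true rate × (1 − share of fevers suppressed at every reading)

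With a true rate of 6.9 % in Group A and in pooled B and C:

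| Masked share, A / B+C | Observed A | Observed B+C | Difference (points) |
|---|---|---|---|
| 30 % / 30 % | 6.9 × 0.70 = 4.8 % | 4.8 % | 0 |
| 13.8 % / 3.6 % (Phase I headache rates as proxy) | 6.9 × 0.862 = 5.9 % | 6.9 × 0.964 = 6.7 % | −0.7 |
| 50 % / 10 % | 6.9 × 0.50 = 3.5 % | 6.9 × 0.90 = 6.2 % | −2.8 |

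For true rates of 5 % to 10 %, the second row gives −0.5 to −1.0 points (5 × 0.102; 10 × 0.102) and the third −2.0 to −4.0 (5 × 0.40; 10 × 0.40). Swapping the masked shares between groups reverses the sign.

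Equal masking leaves the difference unbiased only when the true rates are equal. With assumed true rates of 6.9 % and 3.5 %, a difference of 3.4 points, 30 % masking in both groups gives 3.4 × 0.70 = 2.4 points.

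**4. What a fever-or-any-intake count would do**

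Suppose that every volunteer with headache takes a tablet, headache occurs at Phase I rates, and there is no fever at all. The count would then show 13.8 − 3.6 = 10.2 points between the groups. That far exceeds the biases in step 3, so such a count cannot replace the recorded-temperature table.

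**The case against.** The strongest case against is that little is lost. Temperature is self-recorded twice a day and also measured on site daily at Visits 2–6, so a fever must stay suppressed at every reading to disappear. A volunteer who takes a tablet for headache is still counted among those with general reactions, because headache is itself on the list. Intake is recorded, so the effect can be examined later without any design change. The safety analysis is descriptive, with no test on fever. All of this stands and limits the point to one line of the reactogenicity tables. It does not close the gap: the plan never sets recorded intake against temperature, and a display chosen after unblinding would carry less weight.

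Two stronger readings are tempting, and the documents support neither.

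- A reader might infer that treated fevers are counted as no fever. No section says so, and any reading above 37 °C counts whatever was taken afterwards.
- A reader might infer that more fevers will be hidden in the Quadri group because it has more headache. That needs a real headache difference and headache-driven antipyretic use. The first rests on 4/29 against 1/28, and for the second there are no data. Section 1.3 expects the same safety profile as the trivalent vaccines. Blinding does not rule out symptom-driven use, but it removes the most direct other route to unequal use.

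One could also multiply the headache gap by an assumed share of users who would have been febrile: 10.2 points × 10 %, 30 % or 50 % gives 1.0, 3.1 or 5.1 points. This assumes that the headache difference is real, that every headache leads to a tablet, and that every resulting fever is suppressed throughout. At 50 %, the hidden fever in Group A alone would be 13.8 × 0.5 = 6.9 %, as large as the whole recorded Phase I rate. It is not a usable estimate.

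**Conclusion.** The concern holds in limited form. As written, the plan can understate fever incidence, grade and duration on Days 1–5, and no planned display would show whether it did. Bias in the between-group difference is possible, but its direction and size are unknown. The range of 0 to −4.0 points in the working depends on assumed masked shares, on equal true rates of 5–10 %, and on more masking in Group A. It illustrates scale and is not an estimate. Primary seroconversion, its non-inferiority test and the 193 evaluable or 204 randomized per group are unaffected. This is a cheap improvement to the reporting of a stated study purpose, not a flaw in the design.

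**What to change.** In Section 8.1, before unblinding, keep the recorded-temperature table as the main display and add:

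1. The number and share of volunteers taking any antipyretic, NSAID or anilide on each of Days 0–5, by group, with the recorded reason and the timing relative to the temperature readings where available.
2. A sensitivity table, labelled as such, counting a temperature above 37 °C or antipyretic intake on that day. Show it in two versions: any intake, and only intake recorded for fever or feeling feverish.

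The cost is two descriptive tables from data already collected. The documents do not promise that the reason or clock time of each intake is captured, so the narrower version may be incomplete, and the report should say how often these items are missing. The downside is that the any-intake version counts tablets taken for headache or pain and can itself exaggerate a group difference, so it is supportive only. No change to permitted medication is implied.
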